2 BACKGROUND INFORMATION AND SCIENTIFIC RATIONALE

2.1 Background Information

Over the past decade, community-acquired methicillin-resistant *Staphylococcus aureus* (MRSA) has emerged as a leading cause of hospitalization for children and adolescents in the United States (1). Consequently, the use of antimicrobial agents active against MRSA has become more prevalent (2). Specifically, the use of clindamycin among children hospitalized with *Staphylococcus aureus* infections increased from 21% in 1999 to 63% in 2008. At the same time, rates of childhood obesity have continued to remain high. Recent national data demonstrate that 17% of children aged 2–19 years in the United States are obese (body mass index [BMI] \geq 95th percentile) and 12.3% are morbidly obese (BMI \geq 97th percentile) (3). Obese patients have a greater likelihood of complications from infectious diseases and are at increased risk of developing *Staphylococcus aureus* infections. Therefore, an understanding of the PK of clindamycin in this population is critical to ensure appropriate interventional therapy.

Clindamycin, a semisynthetic antibiotic produced by a 7(S)-chloro-substitution of the 7(R)-hydroxyl group of the parent compound lincomycin (4), is approved by the U.S. Food and Drug Administration (FDA) for the treatment of pediatric and adult patients with respiratory tract, female pelvis and genital tract, and skin and soft tissue infections with susceptible bacteria including streptococci, pneumococci, and staphylococci. Clindamycin is also approved in adults for septicemia and intra-abdominal and serious infections with susceptible anaerobic bacteria (5).

Clindamycin is approximately 90% protein-bound. It is metabolized by the liver and excreted via the liver, bile, and kidneys. Impaired renal function modestly decreases the elimination of clindamycin; however, dosage adjustment is not required with renal dysfunction (4). Clindamycin phosphate (intravenous [IV] formulation) is rapidly converted to active clindamycin which has an elimination half-life of about 3 hours in adults and 2.5 hours in children (5). The drug penetrates well into all tissues, with the exception of the brain and cerebral spinal fluid. It is actively taken up and concentrated within the phagocytic cells. Clindamycin binds to the 50S subunit on the bacterial ribosome and inhibits protein synthesis by interfering with the formation of initiation complexes, thus inhibiting exotoxin production (4). Clindamycin exhibits time-dependent killing; and efficacy is correlated with the time clindamycin concentrations exceed the minimum inhibitory concentration of the pathogen of interest. A summary of clindamycin serum concentrations in non-obese children is found in **Appendix IV**.

Variability in serum and tissue concentrations has been reported in obese patients (4). The underlying premise is that this is due to physiologic changes that alter a drug's volume of distribution (Vd) and body clearance (Cl) (6,7). Thus, obese patients may be dosed inappropriately if fixed or "adult" doses are used (under-dosed) or if weight-based dosing is used (over-dosed) (6,7). Because critically ill obese patients with infections are reported to have a worse outcome than non-obese patients (8), it is imperative to determine if the disposition of and response to clindamycin may be altered compared to healthy children with an infection. In addition, sub-therapeutic drug concentrations may increase the development of resistant

organisms. Thus, it is important to perform pharmacokinetic (PK) and pharmacodynamic (PD) studies in the obese pediatric population to ensure that these patients are being optimally dosed with medications designed to treat infections. There are no currently available PK (or PD) data to guide clindamycin dosing in obese pediatric or adult patients. This proposal will evaluate the safety and PK of clindamycin in obese pediatric patients ages 2 – <18 years.

2.2 Scientific Rationale

Selection of the correct drug dose and dose regimen is the most important decision in ensuring optimal pharmacotherapy. Defining an optimal regimen requires a clear understanding of the drug's PK, PD, and, for many compounds, pharmacogenomic (PG) profiles. Understanding these characteristics for drugs used in pediatrics is imperative to determine optimal dose regimens across the pediatric age continuum.

Clinically, drug dosing in pediatrics is individualized to age by basing the drug dose on a patient's body weight and the dose interval on the functional capacity of the drug's clearance pathways. This approach assumes, though inaccurately, that a drug's V_d and body Cl are directly proportional to a patient's body weight. Despite this lack of proportionality, the majority of pediatric patients favorably respond to weight-based drug dosing. However, as the potency of newer drugs increases and the need for more precise drug dose regimens expands, better-defined dose regimens based on careful assessment of the drugs' integrated PK-PD-PG profiles across the pediatric age continuum are needed (9). Complicating this paradigm are the substantially increasing numbers of children and adolescents who are obese, and even morbidly obese, and the lack of data on disposition in the obese population. Clinical trials of new drugs focused on FDA labeling exclude obese patients, leaving the determination of dosing regimens in the obese for post-marketing, often investigator-initiated studies.

Antibiotic Dosing Regimens Based on PK-PD Modeling

Prior to our understanding of the integrated PK-PD characteristics for antibiotic drugs, antibiotic dosing regimens were mostly based on perceived maximum tolerated doses often related in some manner to the target pathogen minimum inhibitory concentration (MIC). Integration of an antibiotic's PK with PD allows for the determination of the optimal dose regimen across the spectrum of antibiotic drugs (10,11). In addition, this more quantitative approach permits comparisons of different antibiotic drugs for a specific infection and far more accurate predictability of patient response. The specific antibiotic PK-PD characteristic used to predict outcome (i.e., bacteriologic eradication) appears to be mostly dependent on whether the drug's bacterial killing is concentration- or time-dependent. Clindamycin is most often described as a "time-dependent antibiotic with moderate persistent effects," and as such, the best predictor of bacterial killing appears to be the ratio of the area under the clindamycin (free, unbound) drug concentration time curve (AUC) divided by the targeted pathogen MIC (i.e., $fAUC/MIC$) (11). To accurately determine this pivotal PK-PD parameter, what is needed is a comprehensive understanding of the drug's PK profile across the age spectrum while incorporating the spectrum of pathophysiologic changes and differing body habitus. For clindamycin, these data are not available.

Clindamycin Pharmacokinetics

Limited published clindamycin PK data exist and encompass < 100 neonates, infants, and children. In neonates, clindamycin elimination is delayed compared with older infants and

children—mean elimination half-life ($t_{1/2}$) values of 8.7 vs. 3.6 hours, respectively (12,13). Regardless of age group studied, variability was observed in clindamycin $t_{1/2}$, Vd, AND systemic Cl. In addition, some studies report variable serum clindamycin concentrations (bioactivity) following parenteral dosing (12,14). Despite this variation in drug disposition, which is observed in both children and adults, bioactive serum clindamycin concentrations remain therapeutic following routine parenteral (intramuscular, IV) or oral dosing. Considering that clindamycin, an antibiotic, is used to treat infections caused by susceptible pathogens responsible for infectious diseases regardless of patient age, pediatric clindamycin development strategies need only focus on the drug's safety and PK profile to ensure similar systemic exposure. Available clindamycin PK data support close similarity for clindamycin systemic exposure (i.e., bioactive serum clindamycin concentrations and AUC) in older infants, children, and adults following comparable mg/kg doses (12, 14–19). As noted above, clindamycin PK in premature and full-term infants is, as expected, different than that observed in older patients (12,13). This foundation of data underscores the importance of studying clindamycin disposition in the obese pediatric patient.

Clindamycin is extensively bound to plasma protein, primarily to alpha 1 acid glycoprotein, and, with the exception of the brain or cerebrospinal fluid, effectively penetrates body tissues and fluids. The drug is metabolized primarily by the cytochrome (CYP) P450 isoenzyme CYP3A4 to two primary, antimicrobial active metabolites, a sulfoxide and to a lesser extent N-demethylclindamycin (20). Although only limited data are available for current clindamycin pediatric dosing regimens, the regimens employed clinically have been used for decades with apparent success. Nevertheless, clindamycin optimal dosing regimens in pediatrics remain unknown. Furthermore, the influence of obesity on clindamycin disposition is unknown and may have a far greater negative impact on patient outcome due to ill-defined, clinically extrapolated dosing.

Drug Dosing and Obesity

Data defining optimal drug dosing in the obese and morbidly obese adult patient are very limited and virtually non-existent in pediatrics. Drug dosing on total body weight (TBW) in the obese patient has the real risk of overdosing the patient, resulting in an increased incidence of adverse effects, while dosing on ideal body weight (IBW) can lead to serious under-dosing. In obese adults, IBW is increased by 20–40%, which is unaccounted for when using the many mathematical formulas available to calculate dosing based on a person's IBW. This deficiency may partially explain the inaccuracy of drug dose regimens for obese patients based on IBW formula estimations (21–26).

The influence varying degrees of obesity have on important physiologic functions across the age continuum in pediatrics is unknown. In adults, sparse data suggest that obese adults may have altered tissue blood flow rates due to inherent differences in blood flow to lean (greatest amount) and adipose tissue, impaired cardiac function, and alterations in phase I and II metabolism. Although intuitive, one might assume that a drug's Vd would be increased in obese patients for lipophilic compounds, though in fact, for the few drugs assessed, the Vd is highly variable. Similarly, Cl is also highly variable in the obese population, underscoring the need to determine drug disposition characteristics not only across the age continuum but also with increasing degrees of obesity (21–24). No such data are available for the pediatric patient, but these data combined underscore the need to critically assess a drug's disposition relative to age and body habitus. Furthermore, for antibiotics whose efficacy is dependent on achieving

effective concentrations at the infectious site, interfaced with the organism, optimal dosing in the obese pediatric patient must be defined (6,7).

2.3 Potential Risks and Benefits

2.3.1 Potential Risks

Risks of Blood Draws

There are small risks to blood sampling, usually some pain/discomfort with the blood stick. Every effort will be made to avoid additional (to standard of care) sticks for this study by timing clinical blood draws to coincide with timed samples when possible and the use of existing IV lines when feasible for the blood draws.

Risks of Clindamycin

From the FDA label and review of the literature, the following are adverse reactions of clindamycin: antibiotic-associated colitis, pseudomembranous colitis, abdominal pain, nausea, and vomiting; hypersensitivity reactions (maculopapular rash and urticaria have been observed during drug therapy; generalized mild-to-moderate morbilliform-like skin rashes are the most frequently reported of all adverse reactions; rare instances of erythema multiforme, some resembling Stevens-Johnson syndrome, have been associated with clindamycin; a few cases of anaphylactoid reactions have been reported). Organ systems that are affected include skin and mucous membranes (pruritus, vaginitis, and rare instances of exfoliative dermatitis have been reported); liver (jaundice and abnormalities in liver function tests have been observed during clindamycin therapy); renal system (although no direct relationship of clindamycin to renal damage has been established, renal dysfunction as evidenced by azotemia, oliguria, and/or proteinuria has been observed in rare instances); hematopoietic (transient neutropenia [leukopenia] and eosinophilia have been reported; reports of agranulocytosis and thrombocytopenia have been made; no direct etiologic relationship to concurrent clindamycin therapy could be made in any of these instances); local reactions (pain, induration, and sterile abscess have been reported after IM injection and thrombophlebitis after IV infusion); musculoskeletal (rare instances of polyarthritis have been reported); cardiovascular (rare instances of cardiopulmonary arrest and hypotension have been reported following too rapid IV administration). There is minimal additional risk to the participants who are receiving clindamycin as part of their routine medical care.

2.3.2 Known Potential Benefits

The participant may benefit from the use of the study drug; however, participation in this study has no other potential benefits to the participants. The results of this study may benefit overweight and obese participants in the future who require clindamycin therapy.

3 OBJECTIVES

Primary Aim

Characterize the PK of multiple-dose IV clindamycin in overweight and obese children and adolescents.

Secondary Aims

1. Characterize the PK of multiple-dose oral clindamycin in overweight and obese children and adolescents.
2. Characterize the safety profile of clindamycin in overweight and obese children and adolescents.

3.1 Study Outcome Measures

3.1.1 Primary Outcome Measures

1. PK parameters after multiple IV doses of clindamycin:
 - Clearance (Cl)
 - Volume of distribution (Vd)
 - Area under the curve (AUC_{τ})

3.1.2 Secondary Outcome Measures

1. PK results of patients transitioned to oral clindamycin:
 - Oral apparent clearance (Cl/F)
 - Oral apparent volume of distribution (V/F)
2. Safety profile: Adverse events will be collected during and after study drug administration.

4 STUDY DESIGN

This will be a prospective, open-label PK and safety profile study of multiple doses of IV and oral clindamycin in overweight and obese children 2 – < 18 years of age. The total study duration is expected to be approximately 24 months; each participant will participate in the study for up to 18 days (screening day; treatment days 1–14 followed by an observation period of 3 days post discontinuation of clindamycin therapy or after day 17 [on day 18] of therapy in those who are treated with more than 14 days of clindamycin).

REDACTED

5 Study Population

Selection of the Study Population

Eligible participants ages 2 – <18 years will be identified through the inpatient units at each participating site. There will be up to 32 evaluable participants (defined in **Section 10.3**) enrolled; however, target enrollment will be 24 participants. If dosing changes are suggested by the interim PK analysis (see **Section 10.3**), approximately 8 additional participants will be enrolled. Twelve to 16 participants will be enrolled in each of the following age groups: 2–<12 years and 12 – < 18 years of age. Participants will be further stratified into 1 of 2 groups based on their BMI (85th – <95th percentile, and ≥95th percentile). No more than 3 participants with BMI in the 85th – <95th percentile will be enrolled in each age group. Participating sites will prioritize enrollment of participants with BMI >97th percentile in each age group.

5.1 Inclusion/Exclusion Criteria

The investigator or other study site personnel will document in the source documents (e.g., the hospital chart) that informed consent and assent (if applicable) were obtained. Laboratory tests or non-pharmacologic treatment procedures that were performed and considered “routine care” within 72 hours of first dose of study drug may be used for screening procedures required by the protocol and recorded in the case report form (CRF).

Inclusion Criteria

- 1) 2 years – < 18 years of age at the time of first dose of study drug
- 2) Suspected or confirmed infection OR receiving IV clindamycin per routine care
- 3) Negative serum pregnancy test (if female and has reached menarche) within 24 hours prior to first dose of study drug and agreement to practice appropriate contraceptive measures, including abstinence, from the time of the initial pregnancy test through the last dose of study drug
- 4) BMI ≥ 85th percentile for age and sex, based on CDC recommendations
- 5) Obtained informed consent/HIPAA from the parent/legal guardian and assent (if applicable)

Exclusion Criteria

- 1) The following apply only to those who are NOT already receiving clindamycin per routine care:
 - a. History of hypersensitivity or allergic reaction to clindamycin or lincomycin
 - b. History of *C. difficile* colitis with previous administration of clindamycin
 - c. AST > 120 units/L
 - d. ALT > 210 units/L
 - e. Total bilirubin > 3 mg/dL
 - f. Serum creatinine > 2 mg/dL
 - g. Receiving a neuromuscular blocker as part of their therapy (see **Appendix II.B**)
- 2) Previous participation in the study
- 3) Current exposure to medication listed in **Appendix II.A**

- 4) Participant is receiving extracorporeal life support (ECLS)
- 5) Participant is post-cardiac bypass (within 24 hours)
- 6) Participant on inotropes/pressors
- 7) Any other condition or chronic illness that, in the opinion of the principal investigator, makes participation unadvised or unsafe

5.2 Treatment Assignment Procedures

[figure not shown]
This will be an open-label PK study. Participants will be assigned to age groups based on age upon first dose of study drug and to a BMI group based on BMI obtained at baseline (Day 0). The study drug is defined as dose(s) given after consent.

5.2.1 Duration of Study Participation

Duration of therapy will be up to 14 days for children who receive the first dose of IV clindamycin as the study drug. The total duration of therapy with clindamycin will be determined by the treating physician for those children who are receiving clindamycin as part of routine care; however, only 14 days of therapy will be considered as study drug. Study follow-up will occur 3 days (+/- 1 day) after the last dose of study drug. Patients who are receiving antimicrobial agents other than clindamycin may enroll in this study and receive up to 3 doses of IV clindamycin and 4 doses of oral clindamycin in addition to their standard of care therapy. Participants who transition to oral clindamycin may return as outpatients to complete the PK portion of the study.

Total duration of study participation will be up to 18 days. This will comprise a 1-day screening period; a maximum 14-day treatment period; and a 3-day post-study observation period to monitor for serious adverse events. The 3-day post-treatment visit may be a phone follow-up. Patients may continue clindamycin per their physician's recommendation after they have completed participation in this (maximum of) 18-day study.

Figure 2. Timeline

* Minimum of 1 dose of IV clindamycin before IV PK period (see **Section 6.6.2** for further details).

** Minimum of 3 doses of PO clindamycin before PO PK period.

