6 STUDY PROCEDURES

6.1 Summary of Procedures

See the schedule of study events and procedures (**Table 1**).

1. Medical history will be obtained by interview with the parent/legal guardian/participant and from the participant's medical records.
2. Concomitant medications of interest administered within 7 days prior to first study dose and during the period of administration of study drug, including herbal products of interest, will be recorded (see **Appendix II**).
3. Physical examination, including abnormal physical findings, height (measured standing if possible), weight and waist:hip ratio will be obtained (see **Section 6.3 #2**).
4. Safety laboratory testing (see **Section 6.6.1**)
5. PK sampling (see **Section 6.6.2**).

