7.6 Concomitant Medications of Interest/Treatments

Concomitant medications of interest are listed in **Appendix II**. Children who are prescribed one of these medications after receipt of study drug may continue in the study.

REDACTED

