16.2 Data Capture Methods

Clinical data (including AEs and concomitant medications of interest) will be entered into a 21 CFR 11-compliant internet data entry system provided by the DCC. The data system includes password protection and internal quality checks, such as automatic range checks, to identify data that appear inconsistent, incomplete, or inaccurate. Clinical data will be entered directly from the data collection forms/source documents.

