APPENDIX II: MEDICATIONS OF INTEREST

A. Exclusion for ALL participants at the time of enrollment:

- 1) CYP 3A4 potent inhibitors including:
 - a. Cyclosporine
 - b. Erythromycin, clarithromycin
 - c. Itraconazole, ketoconazole
 - d. Ritonavir, delavirdine, protease inhibitors
 - e. Nefazodone, fluoxetine, fluvoxamine
 - f. Verapamil and diltiazem
- 2) CYP 3A4 inducers
 - a. Rifampin,
 - b. Phenytoin
 - c. Ritonavir
- 3) Other: St. John's Wart

B. Exclusion at the time of enrollment (unless the participant was receiving these drugs prior to enrollment AND was receiving clindamycin as part of routine care prior to enrollment):

- 1) Neuromuscular blocking agents: Clindamycin may enhance neuromuscular blocking effect.
 - a. Atracurium
 - b. Cisatracurium
 - c. Pancuronium
 - d. Rocuronium
 - e. Succinylcholine
 - f. Vecuronium

The above drugs are only excluded at the time of enrollment; if a participant begins taking any of the drugs while on-study, he/she will not be discontinued.

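### Children may receive clindamycin on top of another antimicrobial, but the plan does not record that drug, so the safety data cannot reliably identify or describe co-treated children

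*Supplement*

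**What the plan says.** All references are to the latest protocol version in the Supplement.

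- **Co-treatment is planned.** Section 5.2.1 states that "Patients who are receiving antimicrobial agents other than clindamycin may enroll in this study" and that they may "receive up to 3 doses of IV clindamycin and 4 doses of oral clindamycin in addition to their standard of care therapy".
- **Recording is selective.** Section 6.1 asks for "Concomitant medications of interest administered within 7 days prior to first study dose and during the period of administration of study drug". Table 1, the baseline and Days 1–14 lists in section 6.3, the end-of-therapy list in 6.4 and the follow-up contact in 6.5 carry the same restriction. Section 16.2 repeats it for the database: "Clinical data (including AEs and concomitant medications of interest) will be entered".
- **The restriction is defined by a list.** In section 7.6, "Concomitant medications of interest are listed in" Appendix II. Part A of that appendix covers CYP3A4 inhibitors, CYP3A4 inducers and St. John's Wort. Part B covers neuromuscular blockers.
- **Safety is a stated aim.** Secondary aim 2 in section 3 reads "Characterize the safety profile of clindamycin in overweight and obese children and adolescents". Section 10.3 puts everyone with at least one dose of study drug into the safety analysis and gives ALT and AST a dedicated summary of extremes and largest changes. Section 8.2 assesses safety by how often events occur. There is no control group.

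**The concern.** The reactions that section 2.3.1 lists for clindamycin include colitis, vomiting, rash, liver-test changes and neutropenia. All are plausible under many other antibiotics. In a single-arm study of about 24 children, a few events decide what the safety table looks like, so a reader of that table will want to know which children had a second antibiotic on board. The plan expects some children to have one but does not ask for it.

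What is at stake is the interpretability of the aggregate safety summaries. Without a co-treatment field, nobody can describe how common co-treatment was, show events with and without it, or check whether liver-test changes cluster in co-treated children. An analysis plan written later cannot supply data that were never collected.

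**Working it through.** **The plan's one design figure.** Section 10.2 gives a ±16% margin for clearance with 24 participants and a 40% coefficient of variation: 1.96 × 0.40 / √24 = 0.160. It reproduces and does not depend on this point.

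**Tracing the data flow.** The point is about data capture, so the main check sets the instructions side by side.

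1. Section 5.2.1 allows up to 3 IV plus 4 oral clindamycin doses, 7 in all, on top of another antimicrobial.
2. Sections 6.1, 6.3, 6.4, 6.5 and 16.2, and Table 1, record only drugs of interest. Section 7.6 equates these with Appendix II.
3. The only anti-infectives in Appendix II are there because they affect CYP3A4: erythromycin, clarithromycin, itraconazole, ketoconazole, rifampin and certain antivirals. Current exposure to any of them bars entry. They could be recorded only if stopped within the 7-day look-back before entry, or started on study.
4. It follows that the antimicrobial that makes a child an add-on case under section 5.2.1 is not on the list of drugs to be recorded.

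**Whether other collected items fill the gap.**

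- *Prior clindamycin doses* (section 6.3, up to 6) identify children on routine-care clindamycin. They do not distinguish an add-on child from one starting clindamycin alone.
- *Times of study doses* (section 6.3) give a partial clue: no prior clindamycin and no more than 3 IV plus 4 oral doses fits the add-on pattern. A short course of clindamycin alone looks the same. A child on routine-care clindamycin plus a second antibiotic does not fit the pattern at all.
- *Culture results* show organisms, not drugs given.
- *Pertinent medical history* does not require a drug name or dates.

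**How much it could matter.** The documents give neither the co-treated share nor any event rates, so what follows is an illustration under assumptions. Let q be the rate of an event due to clindamycin, b the rate of the same event due to the other drug (acting independently), and f the co-treated share. The pooled rate is

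(1 − f) × q + f × [1 − (1 − q)(1 − b)].

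With q = 10%, the rate in co-treated children is 1 − 0.9 × 0.9 = 19% for b = 10%, and 1 − 0.9 × 0.8 = 28% for b = 20%.

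| f | b = 10% | b = 20% |
|---|---|---|
| 25% | 0.75 × 10% + 0.25 × 19% = 12.3% | 0.75 × 10% + 0.25 × 28% = 14.5% |
| 50% | 0.50 × 10% + 0.50 × 19% = 14.5% | 0.50 × 10% + 0.50 × 28% = 19.0% |
| 100% | 19.0% | 28.0% |

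In 24 children, 10% is 2.4 expected cases and 19.0% is 4.6. The difference is about two children. The dataset could not show which row applies.

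**The case against.** The strongest reply is that attribution is already provided for. The adverse event form records relationship to study drug (section 8.2.3), the investigator applies a causality question (8.4), the medical monitor reviews every serious event when reported (8.5.1), and the DMC reviews data from individual participants (8.8). Site investigators have the chart. This stands. A reader might infer that events in co-treated children cannot be attributed at all, and the documents do not support that. What is missing is the means to identify and describe these children in the analysis dataset.

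A reader might also infer that the short add-on exposure dilutes the event rate because the other drug goes unrecorded. That does not follow: dilution depends on clindamycin dose counts and dates, and section 6.3 collects those.

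Nor would recording the second drug separate its effects from clindamycin's within one child. With no comparator it allows description, a split and a sensitivity check, and the split would be imprecise. If a quarter of 24 children (6) were co-treated and none had an event, the one-sided 95% upper bound would still be 1 − 0.05^(1/6) = 39%.

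Two further replies have weight. No analysis plan is shown, and table splits usually belong there, so the absence of a split is not itself a fault. The CRF and the manual of procedures are not shown either, and one of them could carry an antimicrobial page. Against that, section 16.2 describes the concomitant-medication data as those of interest, and no part of the protocol asks for more.

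Finally, restricting medication capture to drugs relevant to pharmacokinetics or a named interaction is a defensible choice for a Phase I study of an approved drug. It fits less well once the protocol plans co-treatment and makes safety an aim.

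**Conclusion.** The gap is real and limited. As written, the plan lets children receive clindamycin together with another antimicrobial and does not record that antimicrobial. The analysis dataset therefore cannot reliably identify or describe co-treated children, and the pooled adverse event and liver-test summaries cannot be split or checked by co-treatment.

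The size cannot be fixed from the documents because the co-treated share is not stated. Under the assumed rates above, the pooled figure would exceed a 10% clindamycin rate by about 2 to 9 percentage points for co-treated shares of 25% to 50%. This rests on independent effects, on both assumed rates, and on the CRF following the protocol.

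It would be too strong to say that the safety aim fails. Event-level causality remains, the aim is descriptive, and the primary pharmacokinetic outcomes are untouched. This is a worthwhile, inexpensive improvement in data capture.

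**What to change.** Add a recording-only category to Appendix II: systemic antimicrobials other than clindamycin, with drug name, start date and stop date. State that it is not an exclusion. Collect it for all participants from 7 days before the first study dose through the follow-up contact, so that it uses the existing look-back and the existing last contact.

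Present adverse events and liver tests descriptively by any versus no concomitant systemic antimicrobial. This split is preferable to add-on versus other, because it also classifies children on routine-care clindamycin who receive a second antimicrobial. It can be specified in the analysis plan.

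The cost is modest data entry: a few CRF lines per child, taken from the medication administration record that section 7.5 already uses for compliance, and one extra split in the safety tables. No visit, blood draw, eligibility rule or treatment rule changes. The line should be added before or during enrolment, since dates not collected at the time may be hard to recover.
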